2.2. Endpoints

2.2.1. Co-Primary Efficacy Endpoints

2.2.1.1. High Luminance High Contrast (HLHC) Binocular logMAR Visual Acuities

Multiple additional assessments of binocular and monocular visual acuity will be made at all three distances (4m, 64cm and, 40cm) during the study, but the binocular measurements taken at the 2-Week follow-up in the optimized lens pair using high contrast letters in bright illuminance conditions will be the primary endpoint. The logMAR visual acuity scores at each position are continuous co-primary endpoints.

- VA will be evaluated for 3 different distances. At distance (4 meters), VA will be assessed using ETDRS Charts; while near (40 cm) and intermediate (64 cm) assessments will be made using reduced Guillon-Poling charts. Additional visual acuity will be measured using high and low contrast charts in bright illuminance conditions.
- Visual acuity will also be measured using high contrast charts in dim illuminance conditions (created by the use of goggles) . in Appendix H for details regarding the collection of visual acuity (logMAR).

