2.27	Dispensing	Only enough lenses will be dispensed to the subject to wear for the required number of days until their follow-up visit. No spare lenses will be dispensed.	
2.28	Subject Instructions	 Instruct the Subject on the following: The lenses will be worn on a daily disposable wear basis. Instruct the subject to bring back all unworn study lenses. Instruct the subject no cleaning or disinfecting solutions will be used for this lens type. If determined necessary by the Investigator sterile non-preserved rewetting drops may be dispensed to be used as needed for dryness. Subjects will be instructed to wear lenses for a minimum of 6 hours a day, every day between visits. One missed day of lens wear between visits is acceptable. Subjects will be instructed to wear study lenses to the next visit. It is not required that they have worn lenses for 6 hours on the day of the visit. Subjects will be instructed to wear their glasses when not wearing the study lenses. Subjects will be instructed to bring their own spectacles or contact lenses to the 	

	Visit 2: Treatment 1 Follow-Up 1			
Step	Procedure	Details		
		next visit, if needed for exit distance		
		visual acuity measurement.		
2.29	Schedule	The subject will be scheduled to return for		
	Follow-up	their follow-up appointment in 7±1 days.		

VISIT 3

The subjects must present to Visit 3 wearing the study lenses.

Visit 3: Treatment 1 Follow-Up 2			
Step	Procedure	Details	
3.1.	Adverse Events and Concomitant Medications Review	Review any changes to the subject's medical history or concomitant medications from the previous study visit. Record any changes, and any adverse events.	
3.2.	Wear time and Comfortable Wear time (Study Lenses)	Record the average wearing time and comfortable wearing time with the study lenses.	
3.3.	Compliance	Confirm compliance with the prescribed wear schedule.	
3.4.	Collect unworn study lenses (if applicable)	Any remaining unworn study lenses will be collected from the subject.	
3.5.	PRO (CLUE and MRD) Questionnaires	The subject will respond to the Follow-Up PRO (CLUE and MRD) Questionnaires.	
3.6.	Subject Reported Ocular Symptoms	Subjects will respond to a verbal open-ended symptoms questionnaire.	
3.7.	Subjective Acceptance	Record whether the subject's distance and near vision with the lenses is acceptable.	

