3.8.	Entrance Distance and Near Visual Acuity	Record the distance and near Snellen visual acuity (OD, OS, OU) to the nearest letter with the study contact lenses in place. For near measurements use the ETDRS 2000 Series Chart 1 or 2.	
3.9.	Binocular Distance Over-refraction and Distance Visual Acuity	Perform a binocular over-refraction and record the OD and OS results and distance visual acuity. Note: No lens changes are allowed based on the over-refraction.	Appendix G
3.10.	Toric Fit Evaluation	Record:	

	Visit 3: Treatment 1 Follow-Up 2				
Step	Procedure				
		 The rotational position to the nearest degree Lens stability with blink Toric fit acceptable or unacceptable 			
		Toric lens fit will be unacceptable if lenses rotated more than 30 degrees, or lens stability is worse than 5 degrees movement with blink. If toric fit is unacceptable for either eye, the subject will be discontinued from the study. Remove and discard the lenses, then proceed to Final Evaluation.			
3.11.	Lens Fit Assessment	 Evaluate and grade lens centration, primary gaze movement, upgaze movement and tightness (push-up test). Lens fit will be unacceptable if any of the following is observed: presence of limbal exposure (appearance of clear cornea) in any gaze presence of edge lift presence of excessive movement with blink in primary gaze presence of insufficient movement in all three movement categories (primary gaze, upgaze, and push-up test). If lens fit is unacceptable for either eye, the subject will be discontinued from the study. Remove and discard the lenses, then proceed to Final Evaluation. 			
3.12.	Visual Performance Distance (4 M) Intermediate (64 cm) Near (40 cm)	Visual performance will be recorded OD, OS, and OU for the following: Distance, Bright Illuminance ETDRS Charts 4 M-HC#1, HC#2, HC#3 and LC#1, LC#2 and LC#3 Near, Bright Illuminance Reduced Guillon-Poling Charts High Contrast and Low Contrast Intermediate (64 cm) and Near (40 cm).			

	Visit 3: Treatment 1 Follow-Up 2				
Step	Procedure	Details			

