F.4	Exit Distance Visual Acuity	Record the distance Snellen visual acuity (OD, OS, OU) to the nearest letter, and the type of visual correction being worn (habitual lenses, distance spectacles or unaided).			

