8.2. Withdrawal/Discontinuation from the Study

A subject will be withdrawn from the study for any of the following reasons:

- Subject death during the study period.
- Subject withdrawal of consent.
- Subject not compliant to protocol
- Subject lost to follow-up.
- Subject no longer meets eligibility criteria (e.g., the subject becomes pregnant).
- Subject develops significant or serious adverse events causing discontinuation of study lens wear.
- Subjects who have experienced a Corneal Infiltrative Event (CIE).
- Investigator's clinical judgment regarding the subject safety reasons (that it is in the best interest of the subject to stop treatment).
- Subject not compliant with study lens wear schedule.
- Subject not successfully dispensed due to lack of efficacy and safety including poor vision, poor comfort or unacceptable fit.

For discontinued subjects, the Investigator will:

- Complete the current visit (scheduled or unscheduled).
- Complete the Final Evaluation, indicating the reason that the subject was discontinued from the study.
- Record the spherocylindrical refraction with best corrected distance visual acuity.
- Collect used test article(s) (worn or brought to the visit) from the subject and discard them, unless otherwise stated in Section 7.2.
- Collect all unused test article(s) from the subject.
- Make arrangements for subject care, if needed, due to their study participation

An additional subject may be enrolled if a subject discontinues from the study prematurely.

In cases where a subject is lost to follow-up, every possible effort must be made to contact the subject and determine the reason for discontinuation/withdrawal. The measures taken to follow up must be documented including two written attempts and a certified letter (or equivalent) as the final attempt.

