14.5. Primary Analysis

The co-primary efficacy analyses will be conducted on the ITT population, while co-primary safety analyses will be conducted on the safety population. All efficacy and safety analyses will be based on observed case data with no imputation of missing values.

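### At Visit 3 a failed fit sends the subject to Final Evaluation before the co-primary logMAR acuity is taken, while section 8.2 says to complete the visit

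*Combined protocol and SAP*

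**What the plan says.** Section 7.2, Visit 3, sets this order: questionnaires (3.5), entrance Snellen acuity (3.8), over-refraction (3.9), toric fit (3.10), lens fit (3.11), logMAR visual performance (3.12), lens removal (3.13). Steps 3.10 and 3.11 each end with the same instruction when either eye is unacceptable: "the subject will be discontinued from the study. Remove and discard the lenses, then proceed to Final Evaluation". Step 3.12 comes next: "Visual performance will be recorded OD, OS, and OU for the following", at 4 m, 64 cm and 40 cm.

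Section 8.2 lists the investigator's duties for a discontinued subject. The first is "Complete the current visit (scheduled or unscheduled"; completing the Final Evaluation follows as a separate item. The list defers to section 7.2 only in the item on used lenses.

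Section 2.2.1.1 defines the acuity endpoint as "the binocular measurements taken at the 2-Week follow-up in the optimized lens pair using high contrast letters in bright illuminance conditions". Section 14.5 analyses efficacy on the ITT population and adds: "All efficacy and safety analyses will be based on observed case data with no imputation of missing values". Section 14.9 repeats the no-imputation rule and allows early drop-outs to be replaced so that at least 140 complete.

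**The concern.** For a subject who fails fit at Visit 3, sections 7.2 and 8.2 lead to different data. Under 7.2 the lenses come out and step 3.12 is never reached; under 8.2 the visit is finished and the acuity exists. With up to 16 sites (section 4.3), the same case may be handled both ways.

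Under the 7.2 reading, whether acuity is measured depends on how the lens performed. An unstable or strongly rotated toric lens is likely to give worse acuity, so the loss is expected to flatter the lens on the three co-primary acuity tests. That direction is not certain: the endpoint is binocular, and some fit failures need not reduce acuity. An analysis labelled ITT would in practice omit these subjects, and replacing drop-outs would tend to add subjects whose fit held.

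**Working it through.** **Can the endpoint be recovered elsewhere?**

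- Step 3.8: "Record the distance and near Snellen visual acuity (OD, OS, OU) to the nearest letter with the study contact lenses in place". This is Snellen, at distance and near only, so there is no 64 cm value and no logMAR chart score.
- Step 3.9 adds only a distance acuity taken with the over-refraction.
- Final Evaluation step F.4 is distance Snellen with the "type of visual correction being worn (habitual lenses, distance spectacles or unaided".

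None of these is the endpoint. CLUE is safe, because at step 3.5 "The subject will respond to the Follow-Up PRO (CLUE and MRD) Questionnaires", ahead of the fit checks. Slit-lamp findings are covered by F.2, and the two rotation endpoints are read at Visit 1. A subject failing 3.10 would, however, also skip the Visit 3 lens-fit assessment at 3.11, which feeds the unacceptable-fit co-primary.

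**Plan's own figures.** A one-sample t-test at one-sided 0.025 with the Table 7 means and SDs gives power of 99.14% (distance, n = 9), 99.53% (intermediate, n = 6) and 99.11% (near, n = 29). Table 6 states 99.1, 99.5 and 99.1, so it reproduces.

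**Inputs.**

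| Distance | Mean (SD), Table 7 | Threshold | Margin |
|---|---|---|---|
| 4 m | −0.13 (0.078) | 0.00 | 0.13 |
| 64 cm | −0.05 (0.092) | 0.17 | 0.22 |
| 40 cm | 0.07 (0.120) | 0.17 | 0.10 |

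The eye correlation ρ is 0.70 and the number of completers is 140 (both section 14.2). The per-eye failure rate p at Visit 3 is not given. I assume 1%, borrowing the 99% worst case for blink stability in section 14.2, and 5% as a stress value. The acuity deficit d of affected subjects is assumed to be 0.1 to 0.3 logMAR.

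**Subjects affected.** The chance that at least one eye fails is f = 1 − [(1 − ρ)(1 − p)² + ρ(1 − p)].

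- p = 1%: 1 − [0.3 × 0.9801 + 0.7 × 0.99] = 0.01297, or 1.8 of 140.
- p = 5%: 1 − [0.3 × 0.9025 + 0.7 × 0.95] = 0.06425, or 9.0 of 140.

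**Bias in the mean.** This is f × d.

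- p = 1%: 0.01297 × (0.1 to 0.3) = 0.0013 to 0.0039.
- p = 5%: 0.06425 × (0.1 to 0.3) = 0.0064 to 0.0193.

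**Tipping point.** Let 140 − k subjects have the Table 7 mean and SD, give the other k a common value v, and run a one-sample t-test on all 140. For distance with k = 2 and v = 3.64, the mean is (138 × −0.13 + 2 × 3.64)/140 = −0.076, the SD is 0.456 and t is −1.98. One-sided p reaches 0.025 at:

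| Missing | Distance | Intermediate | Near |
|---|---|---|---|
| 2 of 140 | 3.64 | 6.36 | 2.90 |
| 9 of 140 | 1.09 | 2.02 | 0.97 |

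**Error if the true mean equals the threshold, p = 1%.** This is Φ(−1.96 + bias/SE), with SE = SD/√(140 × (1 − f)).

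| Distance | SE | One-sided error, nominal 2.5% |
|---|---|---|
| 4 m | 0.00664 | 3.9% to 8.5% |
| 64 cm | 0.00783 | 3.6% to 7.2% |
| 40 cm | 0.01021 | 3.3% to 5.7% |

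**The case against.** **The conflict may be softer than it looks.** Section 8.2 is a general list for any discontinuation at any visit. Read literally, it would have a subject who fails fit at Visit 1 go on to dispensing, so it may mean only that the visit should be closed out, with the step text governing. That is a fair reading, but no passage states it. It also leaves the larger point intact: if the step text governs, a fit failure always removes the acuity.

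**The effect is very small.** The smallest margin, 0.10, is about 25 times the largest bias at the 1% rate. The 1% itself comes from an endpoint read at Visit 1, subjects reaching Visit 3 have already met the dispensing fit criteria at two visits, and Table 7 shows 100% stability and 0.0% unacceptable fit. The 5% rate has no source. All this stands. Against it, section 14.2 says this is the first dispensing study since the design change, so the Visit 3 failure rate in wear is not known.

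**The error figures stack assumptions.** They need a true mean exactly on the threshold and a binocular loss in every affected subject. In the same model both eyes fail in 0.01² + 0.7 × 0.01 × 0.99 = 0.00703 of subjects, so about 46% of affected subjects keep one acceptable eye. If only bilateral failures cost acuity, the bias is 0.0007 to 0.0021 and the error 2.9% to 4.0% (near) or 3.2% to 5.0% (distance). The tipping points also use a t-test and not the planned mixed model. These are limits on precision.

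**Reordering Visit 3 does nothing for fit failures at Visits 1 and 2.** True; only the sensitivity analysis reaches those subjects.

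**Conclusion.** The concern holds. The two instructions differ, nothing ranks them, and under the step text three co-primary endpoints lose exactly the subjects whose lens fit failed. It is not a power problem and would not change pass or fail at the planning means: two missing subjects would need acuities of 2.9 logMAR or worse, and nine would need about 1.0 or worse. It would matter with a Visit 3 failure rate well above the assumed 1%, or with a true mean near its threshold. The sizes rest on assumed failure rates and an assumed deficit of 0.1 to 0.3 logMAR; the step order and the conflict rest on the text alone. It should be corrected because the correction is cheap, though the trial's conclusion is unlikely to depend on it.

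**What to change.** 1. Reconcile steps 3.10 and 3.11 with section 8.2, so that one instruction says whether step 3.12 is done for a subject who fails fit at Visit 3.
2. For endpoint collection, record the binocular high-luminance, high-contrast logMAR acuity at the three distances before the Visit 3 fit evaluations. This changes measurement order only; the fit criteria and the discontinuation rule stay as written.
3. Unless the stand-alone SAP announced in section 14.1 (not among these documents) already has one, pre-specify a tipping-point analysis of the three acuity means. It should cover ITT subjects with no Visit 3 logMAR value because of discontinuation for fit, vision or comfort, and report how much worse their acuity must be before the one-sided p-value reaches 0.025.

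The cost is a reordered visit, in which lenses come out at step 3.13 for everyone else anyway, and one extra table. The downside is some additional lens wear, probably a few minutes, for an affected subject.

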7.3. Unscheduled Visits

If, during the investigation, a subject requires an unscheduled visit to the clinical site, the following information will be collected at a minimum:

- Chief complaint prompting the visit. If the reason is an adverse event, the applicable eCRF for the adverse event must be completed and subject record completed as appropriate
- Date and time of the visit and all procedures completed at the unscheduled visit
- Review of adverse event and concomitant medications
- Documentation of any test article dispensed or collected from the subject, if applicable
- Slit lamp findings (using the Slit Lamp Classification Scale)

If the Investigator withdraws a subject from the study, the final study visit case report forms must be completed indicating the reason(s) why the subject was withdrawn. The subject record must be completed documenting the date and primary reason for withdrawal and the study CRA notified.

Any ocular and non-ocular Adverse Events that are ongoing at the time of the study visit will be followed by the Investigator, within licensure, until they have resolved, returned to pre-

treatment status, stabilized, or been satisfactorily explained. If further treatment i.e., beyond licensure is required, the subject will be referred to the appropriate health care provider.

The following information will be collected during an unscheduled visit.

	Unscheduled Visit				
Step	Procedure	Details			
U.1	Reason for	Indicate if the only reason for the visit is that			
	unscheduled visit	the subject requires additional test articles. If			
		the reason is other than resupply of			
		previously dispensed lenses, specify the			
		reason for the visit.			
U.2	Chief Complaints (if	Record the subject's chief complaints for			
	applicable)	reasons for the unscheduled visit.			
U.3	Adverse Events and	Review any changes to the subject's medical			
	Concomitant	history or concomitant medications from the			
	Medications Review	previous study visit. Record any changes, and			
	(if applicable)	any adverse events.			
U.4	Entrance VA (if	Record the distance Snellen visual acuity			
	applicable)	(OD, OS, OU) to the nearest letter, and the			
		type of visual correction being worn (study			
		lenses, habitual lenses, distance spectacles or			
		unaided).			
U.5	Subjective Sphero-	Perform bare-eye subjective spherocylindrical			
	cylindrical	refraction with a phoropter (adopt the			
	Refraction (if	maximum plus to maximum visual acuity			
	applicable)	(MPMVA) approach and use the duo-chrome			
		test for binocular balancing) and record the			
		best corrected distance visual acuity to the			
		nearest letter (OD, OS).			
U.6	Slit Lamp	FDA Slit Lamp Classification Scale will be			
	Biomicroscopy (if	used to grade the findings. If the clearance of			
	applicable)	the fluorescein needs to be expedited,			
		preservative-free saline may be instilled.			
U.7	Dispensing (if	If the subject requires additional lenses to			
	applicable)	complete the wear period and is eligible to do			
		so, provide additional lenses per the			
		dispensing instructions given in the detailed			
		study procedures.			
U.8	Toric Fit	After lens settling, record:			
	Evaluation (if	 The rotational position to the nearest 			
	applicable)	degree			
		Lens stability with blink			
		Lens stability with eye versions			
		- Lons stability with eye versions			

	Unscheduled Visit				
Step	Procedure	Details			
U.9	Lens Fit	Toric fit acceptable or unacceptable Toric lens fit will be unacceptable if lenses rotated more than 30 degrees, or lens stability is worse than 5 degrees movement with blink. If toric fit is unacceptable for either eye, the subject will be discontinued from the study. Remove and discard the lenses, then proceed to Final Evaluation. Evaluate and grade lens centration, primary			
	Assessment (if applicable)	 gaze movement, upgaze movement and tightness (push-up test). Lens fit will be unacceptable if any of the following is observed: presence of limbal exposure (appearance of clear cornea) in any gaze presence of edge lift presence of excessive movement with blink in primary gaze presence of insufficient movement in all three movement categories (primary gaze, upgaze, and push-up test). If lens fit is unacceptable for either eye, the subject will be discontinued from the study. Remove and discard the lenses, then proceed to Final Evaluation. 			
U.10	Exit Visual Acuity (if applicable)	Record the distance Snellen visual acuity (OD, OS, OU) to the nearest letter, and the type of visual correction being worn (study lenses, habitual lenses, distance spectacles or unaided).			

7.4. Laboratory Procedures

None

8. SUBJECTS COMPLETION/WITHDRAWAL

8.1. Completion Criteria

Subjects are considered to have completed the study if they:

- provided informed consent.
- are eligible.
- completed all visits

8.2. Withdrawal/Discontinuation from the Study

A subject will be withdrawn from the study for any of the following reasons:

- Subject death during the study period.
- Subject withdrawal of consent.
- Subject not compliant to protocol
- Subject lost to follow-up.
- Subject no longer meets eligibility criteria (e.g., the subject becomes pregnant).
- Subject develops significant or serious adverse events causing discontinuation of study lens wear.
- Subjects who have experienced a Corneal Infiltrative Event (CIE).
- Investigator's clinical judgment regarding the subject safety reasons (that it is in the best interest of the subject to stop treatment).
- Subject not compliant with study lens wear schedule.
- Subject not successfully dispensed due to lack of efficacy and safety including poor vision, poor comfort or unacceptable fit.

For discontinued subjects, the Investigator will:

- Complete the current visit (scheduled or unscheduled).
- Complete the Final Evaluation, indicating the reason that the subject was discontinued from the study.
- Record the spherocylindrical refraction with best corrected distance visual acuity.
- Collect used test article(s) (worn or brought to the visit) from the subject and discard them, unless otherwise stated in Section 7.2.
- Collect all unused test article(s) from the subject.
- Make arrangements for subject care, if needed, due to their study participation

An additional subject may be enrolled if a subject discontinues from the study prematurely.

In cases where a subject is lost to follow-up, every possible effort must be made to contact the subject and determine the reason for discontinuation/withdrawal. The measures taken to follow up must be documented including two written attempts and a certified letter (or equivalent) as the final attempt.

9. PRE-STUDY AND CONCOMITANT INTERVENTION/MEDICATION

Concomitant medications will be documented during screening and updated during the study. Disallowed medications and therapies are medications or therapies that contraindicate contact lens wear. See the Exclusion criteria for specific details.

9.1. Systemic Medications

Certain systemic medications are known to have a higher likelihood to interfere with contact lens wear, chiefly by disrupting the tear film. A summary of disallowed medications is shown in Table 4. Subjects with a history of taking these medications will be allowed to enroll only if:

• The medications have been taken on a continual or routine basis for at least 6 months and the subject has demonstrated successful contact lens wear during this time.

Or

• The subject previously used these medications on a temporary basis and has ceased that medication at least 1 week prior to signing the informed consent.

Class of Drug	Common Indication(s)	Common Examples
Anticholinergics	Irritable bowel syndrome, Parkinson's disease, peptic ulcer, cystitis, nasal congestion, cold symptoms, overactive bladder, COPD	Bentyl, Spiriva, Atrovent, Hyosyne, Levsin, Symax Fastab, Symax SL, Homax SL, Cogentin, Transderm Scop, etc.
Oral Phenothiazines	Antipsychotic disorders (schizophrenia, mania)	Compazine, Mellaril, Thorazine, Phenergan, etc.
Oral/Inhaled Corticosteroids	Arthritis, colitis, asthma, bronchitis, allergic or inflammatory conditions	Cortisone, Prednisone, Hydrocortisone, Medrol, Kenalog, Flonase etc.
Oral Retinoids	Seborrhea, acne	Isotretinoin, Acitretin, Alitretinoin, etc.
Oral Tetracycline	Urinary Tract Infection, acne, chlamydia, gonorrhea	Sumycin, Achromycin V, etc.

Table 4: Disallowed systemic medications

